#### **9.4.      Electrocardiograms**

12-lead ECGs will be obtained at Screening, Pre-dose, Day 1, Day 7, Day 14, and Day 21.

Descriptive summaries will be presented for ECG measures of PR interval, RR interval, mean heart rate, QRS interval, QT interval, and QTcF interval. Corrected QTc intervals will be calculated using Fridericia's correction formula. These summaries will be presented by study visit for the Safety Population overall and by cohort. The mean change from baseline (pre-dose) for each parameter will be plotted by study visit. Values outside the normal range will be flagged in the listings.

The number and percentage of subjects with normal, abnormal but not clinically significant, and abnormal and clinically significant ECG results will be summarized for the Safety population by study visit.

Additionally, QTcF data will be summarized by the following categories by study visit:

- QTcF > 450 msec to  $\leq$  480 msec
- QTcF > 480 msec
- QTcF > 500 msec
- Change from baseline > 30 msec to  $\leq$  60 msec
- Change from baseline > 60 msec

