#### **4.2 Exclusion Criteria**

Subjects who meet any of the following criteria will be excluded from participation in the study:

1. Prior or ongoing medical condition or any abnormal finding on the Screening visit physical exam, ECG, laboratory testing that, in the Investigator's opinion, could adversely affect the safety of the subject or the conduct of the study assessments.
2. Any neurological abnormality other than ET upon neurological exam, including dystonia, ataxia, or any other neurodegenerative disease, including multiple sclerosis or Parkinson's disease.
3. Commercially Confidential Information
4. Significant cognitive impairment or dementia that, in the opinion of the Investigator, would interfere with participation in the study.
5. Commercially Confidential Information
6. Commercially Confidential Information
7. An unstable thyroid condition that, per the Investigator's judgment based on medically significant abnormality of thyroid function testing at Screening. Note: an abnormal TSH level at Screening can be followed by reflex testing of thyroid hormones (T3, T4), if needed, per the Investigator's judgment.
8. History of, or evidence of psychogenic tremor at Screening.
9. Commercially Confidential Information
10. Commercially Confidential Information

11. History of anaphylaxis or hypersensitivity reactions to any of CAD-1883 excipients.
12. Alkaline phosphatase, aspartate aminotransferase (AST), and/or alanine aminotransferase (ALT) level  $>2.5 \times$  upper limit of normal (ULN) at Screening and/or at Baseline/Pre-dose.
13. Serum creatinine  $>120 \mu\text{mol/L}$  and/or creatinine clearance  $<60 \text{ mL/min}$  (according to Cockcroft-Gault formula) at Screening and/or at Baseline/Pre-dose.
14. Total bilirubin  $>2.0 \times$  ULN at Screening and/or at Baseline/Pre-dose. Note: isolated bilirubin  $>2.0 \times$  ULN is acceptable if bilirubin is fractionated and direct bilirubin is  $<35\%$ .
15. Exclusionary ECG abnormalities:
  - a. History of Long QT syndrome and/or QTcF (Fridericia's correction) interval  $>450 \text{ msec}$  (males) or  $>470 \text{ msec}$  (females) per 12-lead ECG done at Screening.

Commercially Confidential Information

16. Commercially Confidential Information

17. History of Alcohol Use Disorder per Diagnostic Statistical Manual of Mental Disorders, Fifth Edition (DSM-V) criteria.

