#### 11.2.1 Analysis of Primary (Safety) Endpoint Data

- Vital sign parameters outside the normal range will be listed and flagged for review.
- Orthostatic vital signs parameters for blood pressure outside the ranges specified in [Section 7.10](#) below will be listed and flagged for review.
- Descriptive statistics of absolute and change from Baseline (pre-dose) SBP, DBP, pulse rate, respiratory rate, and oral temperature at each timepoint, will be tabulated. The mean change from Baseline data will also be plotted across time.
- Twelve-lead ECG parameters will be listed with any values outside the normal range flagged. Descriptive statistics of absolute and change from Baseline (pre-dose) heart rate, PR, QRS, QT, and QTcF intervals at each timepoint, will be tabulated. The mean change from Baseline data will also be plotted across time.
- In addition, frequencies of QTcF data will be calculated according to the following categories:

For absolute values

- QTcF >450 msec (males) and >470 msec (females)
- QTcF >480 msec
- QTcF >500 msec

For change from Baseline

- QTcF increase >30 msec
- QTcF increase >60 msec

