**Same shell as Table 14.3.5.1.1**

**Programming Note:** Visits include Screening, Baseline, Day 1, Day 7 Pre-Dose, Day 7 Post-Dose, Day 14 Pre-Dose, Day 14 Post-Dose, and Day 21; parameters include PR interval (msec), RR interval (msec), mean heart rate (beats/min) QRS interval (msec), QT interval (msec), and QTcF interval (msec); SOURCE: Listing 16.2.8.4.2

Table 14.3.6.2.2  
Summary of 12-Lead Electrocardiogram Interpretation by Study Visit  
Safety Population

Study Visit Category	Cohort-1 (N=XX) n (%)	Cohort-2 (N=XX) n (%)	Overall (N=XX) n (%)
Screening			
Normal	XX (XX.X%)	XX (XX.X%)	XX (XX.X%)
Abnormal, Not Clinically Significant	XX (XX.X%)	XX (XX.X%)	XX (XX.X%)
Abnormal, Clinically Significant	XX (XX.X%)	XX (XX.X%)	XX (XX.X%)
Baseline [1]			
Normal	XX (XX.X%)	XX (XX.X%)	XX (XX.X%)
Abnormal, Not Clinically Significant	XX (XX.X%)	XX (XX.X%)	XX (XX.X%)
Abnormal, Clinically Significant	XX (XX.X%)	XX (XX.X%)	XX (XX.X%)
Day 1			
Normal	XX (XX.X%)	XX (XX.X%)	XX (XX.X%)
Abnormal, Not Clinically Significant	XX (XX.X%)	XX (XX.X%)	XX (XX.X%)
Abnormal, Clinically Significant	XX (XX.X%)	XX (XX.X%)	XX (XX.X%)

Note: Percentages are n/Number of subjects in the Safety Population and respective Protocol Amendment\*100.

[1] The baseline value for each variable is the last observation recorded prior to the first dose of treatment.

SOURCE: Listing 16.2.8.4.1

**Programming note:** Continue for Day 7 Pre-Dose, Day 7 Post-Dose, Day 14 Pre-Dose, Day 14 Post-Dose, and Day 21.

Table 14.3.6.2.3  
Summary of QTcF Values by Study Visit  
Safety Population

Study Visit Category	Cohort-1 (N=XX) n (%)	Cohort-2 (N=XX) n (%)	Overall (N=XX) n (%)
Screening			
QTcF Value			
> 450 msec to ≤ 480 msec [1]	XX (XX.X%)	XX (XX.X%)	XX (XX.X%)
> 480 msec	XX (XX.X%)	XX (XX.X%)	XX (XX.X%)
> 500 msec	XX (XX.X%)	XX (XX.X%)	XX (XX.X%)
Baseline [3]			
QTcF Value			
> 450 msec to ≤ 480 msec [1]	XX (XX.X%)	XX (XX.X%)	XX (XX.X%)
> 480 msec	XX (XX.X%)	XX (XX.X%)	XX (XX.X%)
> 500 msec	XX (XX.X%)	XX (XX.X%)	XX (XX.X%)
Day 1			
QTcF Value			
> 450 msec to ≤ 480 msec [1]	XX (XX.X%)	XX (XX.X%)	XX (XX.X%)
> 480 msec	XX (XX.X%)	XX (XX.X%)	XX (XX.X%)
> 500 msec	XX (XX.X%)	XX (XX.X%)	XX (XX.X%)
QTcF Increase from Baseline [3]			
> 30 msec to ≤60 msec	XX (XX.X%)	XX (XX.X%)	XX (XX.X%)
> 60 msec	XX (XX.X%)	XX (XX.X%)	XX (XX.X%)

Note: Percentages are n/Number of subjects in the Safety Population and respective Protocol Amendment\*100.

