[1] Percentages are based on the number of male subjects in the Safety Population.

[2] Percentages are based on the number of female subjects in the Safety Population.

[3] The baseline value for each variable is the last observation recorded prior to the first dose of treatment

SOURCE: Listing 16.2.8.4.2

**Programming note:** Continue for Day 7 Pre-Dose, Day 7 Post-Dose, Day 14 Pre-Dose, Day 14 Post-Dose, and Day 21.

Table 14.3.6.4  
Summary of Columbia-Suicide Severity Rating Scale (C-SSRS)  
Safety Population

C-SSRS Section C-SSRS Item	Cohort-1 (N=XX)		Cohort-2 (N=XX)		Overall (N=XX)	
	Pre-treatment (N=XX)	Post-treatment (N=XX)	Pre-treatment (N=XX)	Post-treatment (N=XX)	Pre-treatment (N=XX)	Post-treatment (N=XX)
Suicidal Ideation	XX (XX.X%)	XX (XX.X%)	XX (XX.X%)	XX (XX.X%)	XX (XX.X%)	XX (XX.X%)
Wish to be Dead	XX (XX.X%)	XX (XX.X%)	XX (XX.X%)	XX (XX.X%)	XX (XX.X%)	XX (XX.X%)
Non-Specific Active Suicidal Thoughts	XX (XX.X%)	XX (XX.X%)	XX (XX.X%)	XX (XX.X%)	XX (XX.X%)	XX (XX.X%)
Active Suicidal Ideation with Any Methods	XX (XX.X%)	XX (XX.X%)	XX (XX.X%)	XX (XX.X%)	XX (XX.X%)	XX (XX.X%)
Active Suicidal Ideation with Some Intent	XX (XX.X%)	XX (XX.X%)	XX (XX.X%)	XX (XX.X%)	XX (XX.X%)	XX (XX.X%)
Active Suicidal Ideation with Specific Plan	XX (XX.X%)	XX (XX.X%)	XX (XX.X%)	XX (XX.X%)	XX (XX.X%)	XX (XX.X%)
Suicidal Behavior	XX (XX.X%)	XX (XX.X%)	XX (XX.X%)	XX (XX.X%)	XX (XX.X%)	XX (XX.X%)
Actual Attempt	XX (XX.X%)	XX (XX.X%)	XX (XX.X%)	XX (XX.X%)	XX (XX.X%)	XX (XX.X%)
Subject Engaged in Non-Suicidal Self-Injurious Behavior	XX (XX.X%)	XX (XX.X%)	XX (XX.X%)	XX (XX.X%)	XX (XX.X%)	XX (XX.X%)
Interrupted Attempt	XX (XX.X%)	XX (XX.X%)	XX (XX.X%)	XX (XX.X%)	XX (XX.X%)	XX (XX.X%)
Aborted Attempt	XX (XX.X%)	XX (XX.X%)	XX (XX.X%)	XX (XX.X%)	XX (XX.X%)	XX (XX.X%)
Preparatory Acts or Behavior	XX (XX.X%)	XX (XX.X%)	XX (XX.X%)	XX (XX.X%)	XX (XX.X%)	XX (XX.X%)
Suicidal Behavior	XX (XX.X%)	XX (XX.X%)	XX (XX.X%)	XX (XX.X%)	XX (XX.X%)	XX (XX.X%)

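### SAP 9.4 and Table 14.3.6.2.3 replace the protocol's sex-specific QTcF limits (450 msec in men, 470 msec in women) with one row not split by sex, and the shell tags that row with a male-only denominator

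*SAP*

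**What the plan says.** **Protocol.** Section 11.2.1 (and the synopsis) lists the absolute QTcF categories to be tabulated as frequencies. The first is a single bullet, "QTcF >450 msec (males) and >470 msec (females", followed by above 480 and above 500 msec. The bullet names no denominator and no row layout. The same two limits appear in exclusion criterion 15a, "History of Long QT syndrome and/or QTcF (Fridericia's correction) interval", which applies to the Screening ECG.

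**SAP text.** Section 9.4 states "Additionally, QTcF data will be summarized by the following categories by study visit". Its absolute categories are above 450 up to 480 msec, above 480 msec and above 500 msec. None depends on sex.

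**SAP table shell.** In Table 14.3.6.2.3 the first row is labelled "> 450 msec to ≤ 480 msec [1", so it carries footnote [1]. Three statements about denominators sit below the table:
- the general note: "Percentages are n/Number of subjects in the Safety Population and respective Protocol Amendment";
- the first footnote: "1] Percentages are based on the number of male subjects in the Safety Population";
- the second footnote: "2] Percentages are based on the number of female subjects in the Safety Population".

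The second footnote is attached to no row. The rows are drawn for Screening, Baseline and Day 1, and the programming note repeats them: "Continue for Day 7 Pre-Dose, Day 7 Post-Dose, Day 14 Pre-Dose, Day 14 Post-Dose, and Day 21".

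**SAP general rule.** Section 4.1 says that by-visit displays use as denominator the subjects who have a value at that visit.

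**The concern.** Two things look wrong. First, the protocol's sex-specific category has gone and its replacement does not contain it. A reader looking for the planned frequency of men above 450 and women above 470 msec would not find it in the only QTcF category table.

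Second, the replacement row is for both sexes by its label and for men by its footnote. A programmer following the shell as written could count women in the numerator and divide by the number of men, which is not a valid percentage. The unused female footnote points to an incomplete edit, although that is inference.

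At stake is a descriptive safety summary for a new compound, and whether two programmers given the same shell would produce the same numbers.

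**Working it through.** The documents give no count or percentage on this point, so there is no figure of the plan's own to reproduce. The check compares the categories and then illustrates the size.

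**Step 1. Who falls where.** Rules: protocol 11.2.1 (men >450, women >470); SAP row (>450 to ≤480); SAP >480 row.

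| Example (msec) | Protocol first category | SAP row, both sexes | SAP row, men only | SAP >480 row |
|---|---|---|---|---|
| Man, 455 | yes | yes | yes | no |
| Man, 485 | yes | no | no | yes |
| Woman, 460 | no | yes | no | no |
| Woman, 475 | yes | yes | no | no |
| Woman, 485 | yes | no | no | yes |

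**Step 2. Can the protocol category be rebuilt from the rows?**
- Row counts both sexes: (>450 to ≤480) + (>480) = everyone above 450. The protocol category equals that sum minus the women above 450 and up to 470. The table does not give that number.
- Row counts men only: the sum is men above 450 plus women above 480. The protocol category equals that sum plus the women above 470 and up to 480. The table does not give that number either; the woman at 475 is in no absolute row.

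The change-from-baseline rows behave differently. The SAP's (>30 to ≤60) plus (>60) equals the protocol's >30, so re-banding lost nothing there.

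**Step 3. Size of the denominator effect.** Input from the documents: about 30 subjects (Protocol 11.2.4). Assumptions, not in the documents: 20, 15 or 10 of the 30 are men, and every subject has a QTcF value at the visit.

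A count of both sexes divided by men, relative to the same count divided by everyone, is 30/men: 30/20 = 1.5, 30/15 = 2.0, 30/10 = 3.0. One subject adds 1/20 = 5.0%, 1/15 = 6.7% or 1/10 = 10.0%, instead of 1/30 = 3.3%. This compares two denominators for the SAP row; it does not compare that row with the protocol category.

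Illustration with one man at 455, one woman at 460 and one woman at 475 msec:

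| Way of counting | 20 men | 15 men | 10 men |
|---|---|---|---|
| SAP row, both sexes over men (literal) | 3/20 = 15.0% | 3/15 = 20.0% | 3/10 = 30.0% |
| SAP row, men over men | 1/20 = 5.0% | 1/15 = 6.7% | 1/10 = 10.0% |
| SAP row, both sexes over all | 3/30 = 10.0% | 3/30 = 10.0% | 3/30 = 10.0% |
| Protocol category, combined over all | 2/30 = 6.7% | 2/30 = 6.7% | 2/30 = 6.7% |
| Split by sex: men over men | 1/20 = 5.0% | 1/15 = 6.7% | 1/10 = 10.0% |
| Split by sex: women over women | 1/10 = 10.0% | 1/15 = 6.7% | 1/20 = 5.0% |

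**Step 4. Is the information lost altogether?** No. Listing 16.2.8.4.2 shows QTcF by subject and visit but has no sex column; Listing 16.2.4.1 has sex. Joining them by subject recovers the protocol counts by hand.

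**The case against.** The strongest reply is that little turns on this. The table is descriptive, the trial has about 30 subjects, and every QTcF value is listed. If the row counts both sexes over all subjects, everyone in the protocol category still appears in some absolute row. The only surplus is women above 450 and up to 470 msec, which is the cautious direction for safety. All of this stands, and it is why the point is minor.

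A second reply concerns the footnotes. The SAP uses numbered footnotes to override a table's general note: in Table 14.1.2.1 the note uses the whole Safety Population and footnote [1] moves one row to female subjects. By that convention footnote [1] governs the QTcF row, and the general note covers the rest. This also stands, so the table should not be described as giving the row two conflicting denominators. What remains is narrower: a male-only footnote on a row whose label is not restricted to men.

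A third reply is that the protocol never asked for two rows or for sex-specific denominators. That is correct. One combined category over all subjects would fit its bullet. Separate denominators are my reading of the protocol limits together with the two existing footnotes; they are not protocol wording.

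None of these replies restores the 470 msec limit to the table or makes footnote [1] fit the row it is on.

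**Conclusion.** The point holds as a minor correction. The SAP's QTcF table omits the sex-specific category planned in Protocol 11.2.1, its rows cannot rebuild it, and the substituted row carries a footnote that makes its percentage invalid if followed literally. That part rests on the text alone. The factor of 1.5 to 3.0 rests on assumed sex splits and arises only if both sexes are counted over men.

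A reader might infer more than the documents support:
- *That the primary endpoint is affected.* The QTcF categories sit under the protocol's primary safety heading, but the primary endpoint is the occurrence and severity of treatment-emergent adverse events. No hypothesis test uses these rows.
- *That the change was undeclared.* The visible text of SAP section 10 does not mention it, but part of that section is redacted, so this cannot be said.
- *That women between 450 and 470 msec are wrongly counted because they are eligible.* Criterion 15a is a Screening limit and does not make a post-dose rise into that range unremarkable. The row differs from the protocol category; it is not a misclassification against the entry criterion.
- *That every cell of the row is wrong.* The row recurs at each visit and in three columns, but that describes the layout. A cell with no events is zero whichever denominator is used.

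**What to change.** In SAP 9.4 and Table 14.3.6.2.3, replace the first absolute category with two rows:
- QTcF above 450 msec in men, with footnote [1];
- QTcF above 470 msec in women, with footnote [2].

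Define each denominator as subjects of that sex in the cohort with a QTcF value at the visit, in line with SAP 4.1. For the rows above 480 and above 500 msec, use all subjects with a QTcF value at the visit, and amend the footnotes and general note to say so. If the band above 450 up to 480 msec was a deliberate choice, it can stay as an extra row for both sexes, but footnote [1] must come off it.

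The cost is one row becoming two and small edits to notes that already exist. No further ECGs or data are needed. The edit does not settle which of the serial post-dose ECGs represents a visit; that is a separate question.

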#### **9.5.      Further Safety Evaluations**

##### **9.5.1.    Physical Examination**

A complete physical examination (PE) will include general observations; head, eyes, ears, nose, throat, and musculoskeletal. Physical examinations will be conducted at screening, Pre-dose, Day 1, Day 7, Day 14, and Day 21. All physical examination results will be listed.

##### **9.5.2.    Neurological Examination**

Neurological examinations will include assessment of mental status, cranial nerves, motor, sensory, reflexes, coordination, and gait. Neurological examinations will be conducted at screening, Pre-dose, Day 7, Day 14, and Day 21. All results will be listed.

##### **9.5.3.    Columbia Suicide Severity Rating Scale**

The C-SSRS is a questionnaire that prospectively assesses Suicidal Ideation and Suicidal Behavior. At the Pre-dose visit, the "baseline" version of the C-SSRS will be administered. This version assesses Suicidal Ideation and Suicidal Behavior during the subject's lifetime and during the past 12 months. At the Day 14 and Day 21 visits (and the Early Termination visit for subjects withdrawing early), the "since last visit" version will be administered.

Suicidality data collected on the C-SSRS will be listed for all subjects in the Safety Population. Tables will include results from the Suicidal Ideation and Suicidal Behavior sections of the C-SSRS. Frequencies and percentages of subjects with a response of "Yes" at any point on the

Suicidal Ideation and Suicidal Behavior items will be summarized for the Safety Population (overall and by cohort).

Commercially Confidential Information

## **9.7 Kidney safety Composite Measure Biomarker**

The following 6 kidney safety composite measure biomarkers were tested using urine sample: uCreatine (uCr), uClusterin (uCLU) , uCystatin-C (uCysC), uKidney Injury Molecule-1 (uKIM-1), u N-Acetyl-beta-D-Glucosaminidase (uNAG), Neutrophil Gelatinase-Associated Lipocalin (uNGAL) and uOsteopontin (uOPN). Measured concentration is first normalized by dividing it by the concentration of uCR at the same timepoint. The fold change from baseline at a given timepoint is then calculated using the normalized concentration at a time point divided by the normalized concentration at baseline. For example, the normalized uCysC concentration at a given timepoint is calculated as the concentration of CysC at that timepoint divided by the concentration of uCr at the same timepoint. The uCysC fold change from baseline at a given timepoint is calculated as the normalized CysC concentration at a given timepoint divided by the normalized uCysC concentration at baseline. Similar calculations apply to other composite measures.

Commercially Confidential Information

Commercially Confidential Information

## **10. Changes from the Protocol-Planned Analysis**

TETRAS scores from both the central rater and local raters will be summarized. all rating scores will be listed.

Commercially Confidential Information

## **11. Other Planned Analysis**

Commercially Confidential Information

### 13. Tables, Listings, and Figures

All listings, tables, and figures (TLFs) will have a header showing the sponsor company name and protocol on the left (Cadent Therapeutics, CAD1883-201) and Page x of y on the right, and a footer showing the version of SAS, the file name and path, and the source of the data (CRF page or listing number) on the left and production run date in DDMMYY HH:MM on the right.

Summary statistics will be presented to the following degree of precision unless otherwise specified:

Statistics	Degree of Precision
Mean, Median, Quartiles, Confidence limit boundaries	One more than the raw data, up to 3 decimal places.
Standard deviation, Standard error	One more than the mean, up to 3 decimal places.
Minimum, Maximum	The same as the raw data.
p-value	Rounded to 3 decimal places and therefore presented as 0.xxx; p-values smaller than 0.001 as "<0.001"; p-values greater than 0.999 as ">0.999".
Percentage	One decimal place. A percentage of 100% will be reported as 100%. Percentages of zero will be reported as 0.

For weight, height, CCI one decimal place will be used for all summary statistics. Fractional numeric values will be presented with a zero to the left of the decimal point (for example, 0.12 – 0.30).

For summary tables when there are no subjects in a given treatment group/time point, display 0 in the "n" row and leave the statistics blank.

For the AEs by SOC and PT, sort the SOC by alphabetical order and sort the PT under SOC by decreasing frequency in the cohort, unless specified otherwise.

If there is a missing value for any categorical analysis, add a "Missing" category as the last one for the variable.

### 13.1. Planned Table Descriptions

The following are planned summary tables for protocol number CAD1883-201. The table numbers and page numbers are place holders only and will be determined when the tables are produced.

**Table 4: Demographic Data Summary Tables and Figures**

Number	Population	Title
Table 14.1.1	All Enrolled Subjects	Subject Disposition
Table 14.1.2.1	Safety	Demographics and Baseline Characteristics
Table 14.1.2.2	Safety	Disease History
Table 14.1.3	Safety	Summary of Medical History by SOC and PT

Commercially Confidential Information

Table 14.1.5.1	Safety	Summary of Treatment Exposure and Compliance via Capsule Counts
		Commercially Confidential Information

### 13.2. Efficacy Data

**Table 5: Efficacy Data**

Number	Population	Title
Table 14.2.1.1.1	FAS/Exposed	Summary of Central Rater TETRAS-PS Scores by Study Visit
		Commercially Confidential Information
Table 14.2.1.1.3	FAS/Exposed	Summary of Central Rater Categorical TETRAS-PS Item Scores by Study Visit
		Commercially Confidential Information
Table 14.2.1.1.5	FAS/Exposed	Summary of Local Rater TETRAS-PS Scores by Study Visit
Table 14.2.1.2.1	FAS/Exposed	Summary of Central Rater TETRAS-PS Upper Limb Subscale Scores by Study Visit
		Commercially Confidential Information

Number	Population	Title
		Commercially Confidential Information
Table 14.2.1.2.4	FAS/Exposed	Summary of Local Rater TETRAS-PS Upper Limb Subscale Scores by Study Visit
Table 14.2.1.3.1	FAS/Exposed	Summary of Central Rater TETRAS-PS Upper Limb Tremor (Item 4) Total Scores by Study Visit
		Commercially Confidential Information
Table 14.2.1.3.3	FAS/Exposed	Summary of Local Rater TETRAS-PS Upper Limb Tremor (Item 4) Total Scores by Study Visit

Commercially Confidential Information

